4.2. Handling of missing data

In case of missing data, this will be handled with an "only complete case analysis". This involves only analyzing data from participants who have completed all study visits and provided all required data. In the sample size calculation we compensated for expected drop-outs (rate of 15%).

5. Regulatory Aspects AND SAFETY

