2.3 Project design

The study is a human research study in which customers that are taking the collagen activator from Avea are observed for six months. The trial is in the form of a post marketing surveillance observational trial since the product has already been approved and is sold on the market. All participants are voluntarily taking the collagen activator. There is no blinding, randomization or placebo control that is taking place in the trial. The results are compared individually for each participant after the follow ups from their baseline measurements.

- The trial exposure is the Collagen activator from Avea
 - Potential participants are contacted after purchasing the collagen activator for 6 months via Avea's online shop. After successful recruitment they undergo the baseline assessment. They are instructed to only start taking the collagen activator once the baseline assessment is completed.
 - o Daily oral intake of 1 package of 11.5g diluted in water over six months, taken in the morning
- Saliva samples are taken twice (time points 0 and +6 months) to determine biological age via epigenetic methylation clock (Trume labs are the test providers and analysers)
- Skin analysis takes place at time points 0, +1 and +3 months to determine skin quality. This includes measurements of hydration, elasticity, skin thickness and density, as well as pigmentation, wrinkles, texture, UV-spots, pores, redness and porphyrins.
- Skin tests used for this are the corneometer, cutometer, ultrascan and Visia scan.
- Every month the participants receive a questionnaire regarding recent subjective changes, adverse reactions and adherence

The individual duration expected for each patient from the recruitment process onwards is about 6-7 months

- The goal is to recruit 60 healthy participants that are older than 35 years and are voluntarily taking the collagen activator for 6 months
- 2-3 weeks from being recruited to receiving a date for the baseline measurements
- Day 1 being the day of the baseline measurements
- Follow ups for the skin measurements take place +1 and +3 months from day 1
- Follow up for the saliva test takes place +6 months from day 1

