3.4 Withdrawal and discontinuation

The Sponsor or Projectleader may terminate the trial prematurely for individual participants or the participants may withdraw from the study according to certain circumstances:

- Participants can withdraw from the study if they have any concerns regarding their health or safety being compromised due to the procedures during the study or if they voluntarily stop to take the collagen activator, which no longer qualifies them to be part of the study.
 - o This includes any adverse reactions to the procedures during the study
 - o Other restrictions or reductions regarding their mental or physical health that is linked to the procedure during the trial
 - o if they withdraw their informed consent
 - o if they voluntarily decide to stop taking the "intervention"
 - Participants can be excluded from the trial in case of non-compliance
 - o Incorrect / irregular intake of the "intervention"
 - o Failing to regularly answer the questionnaire
 - o Missing out or not showing up to the appointments
 - o Not adhering to the required testing procedures

In case a participant has to withdraw or be excluded from the study, their data will not be included in the analysis (sample size is adjusted for a drop-out rate of 15%). There will be no final examination of the participant and the previously gathered material of the participant will be destroyed.

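### A study-wide complete-case rule, together with removal of everyone who leaves or is excluded, restricts every analysis to selected completers, even where the endpoint itself was fully measured

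*Protocol*

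**What the plan says.** Two sections of the protocol fix who is analysed.

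- **Section 4.2** prescribes a complete-case analysis and defines it over the whole study: "This involves only analyzing data from participants who have completed all study visits and provided all required data". It does not say which data are required, or for which endpoint.
- **Section 3.4** states: "In case a participant has to withdraw or be excluded from the study, their data will not be included in the analysis". Reasons for leaving include health concerns and reactions ("This includes any adverse reactions to the procedures during the study"). They also include stopping the product: "if they voluntarily stop to take the collagen activator, which no longer qualifies them to be part of the study".
- **Section 3.4** adds a discretionary route, open to the sponsor or project leader: "Participants can be excluded from the trial in case of non-compliance". The grounds are irregular intake, missed appointments, not following the test procedures, and "Failing to regularly answer the questionnaire". No threshold is given for intake or for answering.
- For those who leave, **section 3.4** continues: "There will be no final examination of the participant and the previously gathered material of the participant will be destroyed".

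Section 2.3 describes a study without blinding, randomisation or placebo, in which each participant is compared with their own baseline: "The trial is in the form of a post marketing surveillance observational trial". Adverse reactions are collected in the monthly questionnaires (2.3, 3.3). No all-enrolled set, safety set or sensitivity analysis is named. The only stated answer to dropout is a larger sample (3.4, 4.1, 4.2).

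**The concern.** Three things are at stake.

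1. **Selection in the main result.** In a single-arm pre-post study the mean change among those retained is the efficacy finding, and no comparison arm shares the same selection. People who persist, tolerate the product and adhere may differ in outcome from those who do not. Planning for dropout keeps the number analysed up but does not make the retained group representative.
2. **Data discarded without a reason tied to the endpoint.** The primary model in 4.1 needs the change in biological age between two saliva samples, plus age and sex. It uses nothing from the month-1 and month-3 skin visits, yet missing one of those visits removes the participant. Conversely, valid skin data from months 0, 1 and 3 are discarded if the month-6 saliva sample is missing.
3. **Non-serious adverse reactions.** Someone who reports a reaction in a monthly questionnaire and then leaves drops out of the analysis. No other stated route carries that report into the results of a study that labels itself surveillance.

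**Working it through.** **The plan's own figures.** Inputs from 4.1: one-sided alpha 0.05, power 0.80, effect size 0.5. A two-sample t-test with these inputs needs 50.15 per group, which matches the stated 50. Dropout inflation: 50/0.85 = 58.8, so 59; 50/0.80 = 62.5, so 63. Both match. The sample is set at 60, so the plan expects 60 × 0.85 = 51 or 60 × 0.80 = 48 analysed, that is 9 to 12 removed. (Section 4.1 gives 15-20% dropout; 3.4 and 4.2 give 15%.)

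**What inflation protects.** A one-sided paired t-test at d = 0.5 has power 0.97 with 51 participants, 0.96 with 48 and 0.92 with 38. Power is not the problem.

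**How many the rule can remove.** Assume each post-baseline item is missed independently with probability p, so that the number retained is 60 × (1 − p)^k.

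- k = 9 counts 2 skin visits, 6 monthly questionnaires and 1 saliva sample.
- k = 7 leaves out the month-1 and month-3 questionnaires, which 3.3 says are checked and if necessary completed at the visit. Baseline items are left out of both counts because they are done at one supervised visit.

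| p (assumed) | k = 9 | k = 7 | Month-6 saliva only, k = 1 |
|---|---|---|---|
| 2% | 60 × 0.834 = 50 | 60 × 0.868 = 52 | 60 × 0.98 = 59 |
| 3% | 60 × 0.760 = 46 | 60 × 0.808 = 48 | 60 × 0.97 = 58 |
| 5% | 60 × 0.630 = 38 | 60 × 0.698 = 42 | 60 × 0.95 = 57 |

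Both counts treat questionnaires as required data, which the protocol leaves open. If missed items cluster within people, fewer participants are lost than shown.

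**How far the estimate could move.** Let f be the share removed, with the retained averaging 0.5 SD. The effect in all enrolled is (1 − f) × 0.5 + f × (effect in those removed).

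- Removed have zero change (assumed): 0.85 × 0.5 = 0.425 at 15%; 0.80 × 0.5 = 0.40 at 20%.
- Removed worsen by 0.5 SD (assumed): 0.425 − 0.15 × 0.5 = 0.35; 0.40 − 0.20 × 0.5 = 0.30.

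**False positives under selection.** In a simulation of 40,000 trials of 60 with no true change, those with the lowest completion score were removed, that score having an assumed positive correlation with favourable change. The one-sided 5% paired test then rejected as follows:

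| Correlation (assumed) | 15% removed | 20% removed |
|---|---|---|
| 0.1 | 7% | 8% |
| 0.3 | 14% | 18% |
| 0.5 | 26% | 35% |

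The protocol gives no value for this correlation. A negative one would push the result the other way.

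**The case against.** The strongest reply has five parts.

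- **The objective concerns six months of intake (2.1).** Without randomisation, an on-product question is defensible. That stands, and it is a reason to keep an adherent set as a supporting analysis. It does not justify dropping a fully adherent participant with both saliva samples because of a missed skin visit.
- **A separate SAP might define analysis sets.** The point is not about something left unsaid: 3.4 and 4.2 state rules, and 4.1 is itself headed as the statistical analysis plan.
- **A reader might infer that one missed questionnaire removes a person automatically.** The text does not establish this. Section 3.4 speaks of regular answering and makes exclusion optional, and 4.2 leaves the required data undefined. Automatic removal is clear only for a missed study visit.
- **A reader might infer that adverse reactions vanish altogether.** They do not. Serious events go to the Ethics Committee within 7 days (5.3), and safety measures are notified separately (5.2). The reaction listed in 3.4 is to study procedures, although stopping the product for a reaction has the same effect on the data. No safety objective or endpoint is set in 2.1 or 2.2. What remains is the gap for non-serious reactions. The material to be destroyed most naturally means biological samples, not recorded data.
- **A reader might infer that the estimate is certainly biased toward benefit.** Participants cannot perceive methylation change and receive their results only after the study (3.2, 6.1). The protocol does not say that whoever decides exclusions sees skin results. The direction is plausible but not shown.

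**Conclusion.** The point holds. Sections 3.4 and 4.2 confine every analysis to people who stayed, were not excluded and completed all visits and required data, whichever endpoint is analysed. A missed skin visit removes a valid primary outcome, and a missing month-6 saliva sample removes valid skin outcomes. In an uncontrolled pre-post study such selection enters the efficacy result directly, and sample-size inflation does not correct it.

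The size depends on assumptions. With 2%, 3% or 5% of items missing independently, about 50-52, 46-48 or 38-42 of 60 remain, against the 48-51 the plan expects. If the 15-20% removed had no change, a retained effect of 0.5 SD corresponds to 0.40-0.43 SD in all enrolled. These are illustrations, not predictions; neither the attrition pattern nor the outcome of those removed can be known from the protocol. The documents do not support a claim of lost power or of a proven direction of bias.

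The rule should be changed before data collection: 3.4 ends follow-up and has gathered material destroyed, so later analysis cannot recover what was lost.

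**What to change.** **Section 4.2.** Replace the study-wide complete-case rule with endpoint-specific sets.

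- Primary endpoint: everyone with a baseline and a month-6 saliva result, regardless of skin visits, questionnaires or adherence.
- Skin endpoints: everyone with a baseline and at least one follow-up measurement. A repeated-measures model over months 0, 1 and 3 would let a participant with only one follow-up contribute.
- Adverse reactions and reasons for leaving: reported for everyone who took the product, including those who withdrew or were excluded.
- Keep the complete-case or adherent set as a sensitivity analysis.

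**Section 3.4.** Keep coded data collected before withdrawal or exclusion unless the participant asks for removal, as far as the consent allows. Separate stopping intake from leaving follow-up, and ask those who stop intake for the month-6 home saliva sample that is already planned. Their baseline sample must then not be destroyed before it is analysed.

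**Cost.** Rewording of two sections and, if needed, a consent sentence on data already collected; the consent text is not available here, so that part cannot be judged. The estimated effect may be smaller. The change reduces selection but does not remove it, because anyone without a month-6 sample still falls outside the primary set.

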5.1 Local regulations / Declaration of Helsinki

This research project will be conducted in accordance with the protocol, the Declaration of Helsinki ³, the principles of Good Clinical Practice, the Human Research Act (HRA) and the Human Research Ordinance (HRO) ¹ as well as other locally relevant regulations. The project leader acknowledges his responsibilities as the project leader

5.2 Notification of safety and protective measures (HRA Art. 15, HRO Art. 20)

If, during the research project, circumstances arise which could jeopardize the safety or health of the participants or lead to a disproportionate relationship between the risks and burdens and the benefits, all the measures required to ensure protection are to be taken without delay.

The Principal Investigator and the Sponsor are promptly notified (within 24 hours) if immediate safety and protective measures have to be taken during the conduct of the research project. The Ethics Committee will be notified via BASEC of these measures and of the circumstances necessitating them within 7 days.

5.3 Serious events (HRO Art. 21)

If a serious event occurs, the research project will be interrupted and the Ethics Committee notified on the circumstances via BASEC within 7 days according to HRO Art. 21.

"A Serious Adverse Event (SAE) is classified as any untoward medical occurrence that:

- results in death
- is life-threatening
- requires in-patient hospitalization or prolongation of existing hospitalization
- results in persistent or significant disability/incapacity, or
- is a congenital anomaly/birth defect.

5.4 Procedure for investigations involving radiation sources

No radiation sources are being used in this project.

5.5 Amendments

Substantial changes to the project set-up, the protocol and relevant project documents will be submitted to the Ethics Committee for approval according to HRO Art. 18 before implementation. Exceptions are measures that have to be taken immediately in order to protect the participants.

5.6 End of project

Upon project completion or discontinuation, the Ethics Committee is notified within 90 days.

5.7 Insurance

In the event of project-related damage or injuries, the Sponsor will be liable, except for damages that are only slight and temporary; and for which the extent of the damage is no greater than would be expected in the current state of scientific knowledge (Art. 12 HRO).

6. FURTHER Aspects

6.1 Overall ethical considerations

Overall ethical considerations of the project:

The primary ethical consideration of this study is ensuring the generalizability and overall social and scientific value of the project. To achieve this, the study will be conducted in healthy adults of both genders and different ethnicities. By ensuring that the study design and procedures are appropriately robust, and that the participant cohort is diverse and representative, the results of the study can be used to inform future research and decision-making in a meaningful and impactful way.

All procedures have been thoroughly justified, and all participants will be provided with clear information regarding their rights, risks, and obligations.

Incidental findings relevant to a person's health will be communicated to all participants, unless they inform us that they do not wish to be informed. They are made aware of this in the study information. Individual study results will be communicated to all participants once the whole study is completed, unless they inform us that they do not wish to be informed. They are made aware of this in the study information.

All participants are informed about the special risks associated with genetic data. In this study saliva samples are collected to determine biological age. For this epigenetic methylation is analyzed as well as 9 short DNA sequences. The saliva samples as well as the DNA sequence data is deleted after the determination of biological age and is not used to generate any health related information of the participants.

Additionally, voluntary study participation will be emphasized throughout the project, and participants will be given the option to decline participation or withdraw from the study at any time, without giving a reason.

Study design and participant burden:

The study design and procedures have been thoroughly justified to ensure that they are reasonable and not overly burdensome for participants. Participants are required to take monthly online questionnaires, two saliva tests and three visits to a skin test center. Participants will be informed of the time and effort required for participation and will be compensated appropriately. At the end of the study they receive all their personal results (if agreed to), for which the tests have a value of approximately 1000 CHF.

Overall fair balance:

In summary, the study design and procedures have been justified, and project-specific ethical aspects have been taken into consideration. Participants will be given the opportunity to make an informed decision about their participation in the study, and their rights and welfare will be protected. The burden and time effort required of participants will be minimized, and they will be compensated for their participation. Overall, there is a fair balance for the study participants.

6.2 Risk-Benefit Assessment

The benefits for participants of the projects are the following:

Participants in this study stand to benefit by receiving information about their biological age and their skin quality, which has the potential to improve their welfare and health awareness. These benefits are not only valuable to participants in the short term, but could also have important long-term health implications. By providing participants with free valuable health information, the study team is helping to promote participant welfare and ensure that the project is conducted in an ethical and responsible manner. There are only minimal risks associated with the intervention participants are exposed to and procedures included in this project. They are addressed in the following section together with the risk minimization:

Avea collagen activator (exposure)

• As of now there are no known adverse reactions associated with the product from any of the early trials and since the product has been on the market, there have been no reports of major adverse effects or reactions.

Skin analysis (Corneometer, cutometer, ultrascan (22Mhz), Visia scan

- Risk minimisation during the recruitment process through screening for any sensitivity regarding exposure to light (sunlight, UV-light etc.)
- A medical professional is accompanying the trial participant during that process and on the lookout for any adverse reactions or complications during the process
- All procedures that are part of the skin analysis are non-invasive. In rare cases they can lead to skin irritation or damage, specifically if they are used too often or with too much pressure, which our study personal will be instructed to avoid.
- All skin tests will not be performed on open wounds or skin infections.

Saliva collection

- The risks are minimized as the sample collection is non-invasive (participant spits on a clean spoon).
- The sample collection is self-administered and participants will be provided with clear and concise instructions on how to collect their saliva sample.

Analysis of saliva samples to determine biological age

- The saliva samples are collectively shipped every week (the samples that are ready) to our collaborator, Trume labs, without risk to the samples as they are stable up to one year under ambient conditions.
- For the analysis, 9 small DNA regions are sequenced, and used to determine the methylation of your DNA. Genetic information is not analyzed.
- After the determination of biological age, the sequence data is deleted and the saliva samples are destroyed. This minimizes the risks of the data being used in any other way or of personal genetic information being revealed.
- The samples are screened upon arrival at Trume labs and in the case that a sample is contaminated or too wet, we will be informed and ask the participant to retake the saliva sample. As we ship the samples every week, in the case that a sample is contaminated it will be possible for the participant to redo the sample within 1 to 1.5 months maximum considering shipping times. The delay of the datapoint will be taken into account for the analysis.

•

Questionnaire

- The private information provided in the questionnaires will be kept confidential, following our protocol for data protection
- Contact details of trial doctor's are provided to the patients for any case of privacy concerns, mental support or language difficulties

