3.1 Project population, inclusion and exclusion criteria

The project population consists of healthy adults over the age of 35 years, regardless of gender or ethnicity, who are willing and able to give their informed consent to participate in the study. The total number of participants will be 60. The choice of participants over 35 years is because in younger individuals collagen is not yet depleted or only to a small extent ⁶. To ensure gender balance in the recruitment, our inclusion criteria are gender-neutral, gender-neutral language is used in all study materials and advertisements and we will engage in diverse recruitment to target a broad population.

Participants fulfilling the following inclusion criteria are eligible to participate in the study:

- Age 35 or older, regardless of gender, ethnicity or socioeconomic background
- Voluntarily purchasing the collagen activator (from Avea) for 6 months with the intend to take it on a daily basis
- Willing to fill out the questionnaires on a monthly basis.
- Willing to participate in all measurements part of the study (Skin tests & saliva samples)
- Able to appear at the baseline, 1 and 3 month follow up visits at the Dermatology clinic "Hautwerk" in Zürich.

If any of the following exclusion criteria are present, the participant will be excluded from the study:

- Underlying health conditions leading to regular intake of medication, including:
 - o Diabetes
 - o Hypertension (high blood pressure)
 - o Cardiovascular disease
 - o Asthma
 - o Chronic obstructive pulmonary disease (COPD)
 - o Arthritis
 - o Depression
 - o Anxiety
 - o Epilepsy
 - o Cancer
 - o Thyroid disorders
 - o Autoimmune diseases such as lupus or multiple sclerosis
 - o Chronic kidney disease
 - o Liver disease
 - o HIV/AIDS
 - o Chronic pain conditions such as fibromyalgia or chronic migraine.
 - 0 ...

- Chronic skin condition, independent of treatment, including:
 - o Acne
 - o Eczema
 - o Psoriasis
 - o Rosacea
 - o Skin cancer
 - ο.
- Intake of any collagen supplements 3 months prior to the screening date
- Smoking at time of recruitment or smoking up to 5 years prior to recruitment
- Pregnancy or lactating at the time of recruitment or planning to get pregnant in the following 6 months
- Insufficient knowledge of the German or English language
- Unable to give consent
- Unable to follow the procedures that are part of the study

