3.2 Recruitment, screening and informed consent procedure

Recruitment will be conducted through advertising the study to Avea customers after they have bought the collagen activator in the Avea online shop for the first time. The advertisement will be uploaded in BASEC.

Potential participants are Avea customers, therefore the Avea team has access to their email addresses. The study advertisement is sent to the email address under which the order was placed. The first round of pre-selection will be done by the potential participants themselves by going through the study advertisement and the description of the trial. If a person decides they are interested in participating, they can fill out the inclusion and exclusion guestionnaire which is attached to the advertisement (via a link to a google form). In this form they enter their email address. For questions they can reach out via email to the person in charge of recruitment at Avea. The results of the google form are only visible to the Avea team member in charge of recruitment. Once that person has decided if a person is eligible to participate according to the criteria defined in section 3.1 (if uncertain the decision is made together with [name]), the answers of the google form are deleted immediately and the email address is transferred to RedCap. From then on they are considered as participants and all information is securely stored and encrypted in RedCap. Via RedCap they then receive the detailed study information. This entails the nature of the study, its purpose, the procedures involved, the expected duration, the potential risks and benefits and any discomfort it may entail. Each subject is informed that the participation in the study is voluntary and that he/she may withdraw from the study at any time and without stating any reason. The withdrawal of consent will not affect his/her subsequent medical assistance and treatment. The subjects are informed that he/she can ask any question, and consult with family members, friends, their treating physicians or other experts before deciding about their participation in the study. Enough time is given to the subjects to make a decision and to give informed consent at all times. The subjects are informed that authorized individuals may examine his/her medical records and how and for which purpose the extracted data will be used.

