Together with the detailed study information they receive a booking link from the Hautwerk clinic (only for the study) where they can schedule their first appointment (within the following 3 weeks) if they remain willing to participate. They can schedule a phone call with [name] to clarify any remaining questions (optional they can also reach out to her via email if there are only a few or no questions).

At the first appointment, each subject will once again fill out the inclusion and exclusion questionnaire to confirm their eligibility for the study. [name] will explain again to each subject what it means to be part of the study (see paragraph above), and will fill out the informed consent form with each participant.

The participants should read, understand, and voluntarily agree before signing and dating the informed consent form, and are given a copy of the signed document. The consent form is signed and dated by the participant and the Project leader Frau [name], or her assigned substitute. The signed consent form is retained as part of the investigation records.

No direct payment is given to the study participants. Each person does receive the skin scans and results of the saliva biological age tests after completion of the study free of charge (information only provided after completion of the study and if the participant has not informed us of not wanting to receive this information).

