- 3. Ultrascan: Ultrascan is a non-invasive device that uses high-frequency ultrasound waves (22 Mhz) to measure the thickness and density of the skin. The device works by emitting ultrasound waves into the skin, which bounce back and are recorded by the device. The time it takes for the ultrasound waves to bounce back is used to calculate the thickness of the skin. This measurement is used to assess the overall health of the skin and collagen content can be read out by it.
- 4. Visia scan: Visia scan is a non-invasive imaging system that captures high-resolution images of the skin's surface. The device uses different types of light, such as UV, polarized, and non-polarized light, to capture images of the skin at different depths. The images are then analyzed to assess various skin conditions, including pigmentation, wrinkles, texture, UV-spots, pores, redness, and porphyrins. This measurement is used to assess the overall health and quality of the skin.

At the time points +1, +2, +3, +4 +5 and +6 months of the study duration, a short online questionnaire will be sent to all participants via email, with a secure link to the REDcap online form. It will contain questions about the product intake (how many days of the months), the health status (any changes, physical or mental illness, adverse reactions), important lifestyle changes, and if the participants are still willing to continue with the study. There will also be the possibility for the participants to reach out to a medical professional or to schedule a visit.

At the timepoints +1 and +3, follow-up visits at the Dermatology clinic Hautwerk will be scheduled (time frame +/- 1 week of the +1 and +3 months time point respectively). The visit will contain the same procedures as the visit at time point 0, minus the saliva sample. The medical professional will again first check the completion of the questionnaire and assist if necessary, then take the skin scan (Visia analysis system), and the tests with the corneometer, cutometer and ultrascan. The participants have then time to rest to make sure there are no adverse reactions to any of the procedures. At time point +3, the participant will be provided with the saliva collection kit for timepoint +6 months. Each visit will be recorded by the medical professional. The total visit should take between 30 to 60 minutes.

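### Section 6.2 counts light-sensitivity screening at recruitment as a protection for the skin analysis, but no criterion in 3.1 and no step in 3.2, 3.3 or the schedule carries it out

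*Protocol*

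**What the plan says.** **Safeguard.** Section 6.2 (Risk-Benefit Assessment), under the skin analysis, lists "Risk minimisation during the recruitment process through screening for any sensitivity regarding exposure to light (sunlight, UV-light etc".

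**Exposure.** Section 3.3 says of the Visia scan: "The device uses different types of light, such as UV, polarized, and non-polarized light". Section 2.3 and the schedule in Appendix 1 place the skin tests at months 0, +1 and +3.

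**Eligibility decision.** Section 3.2 has applicants complete an online inclusion and exclusion form. A member of the sponsor's team then decides eligibility "according to the criteria defined in section 3.1", with a second person consulted if there is doubt. At the first visit, "each subject will once again fill out the inclusion and exclusion questionnaire to confirm their eligibility for the study".

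**Criteria.** In section 3.1 the two exclusions nearest to light sensitivity are headed "Underlying health conditions leading to regular intake of medication, including" and "Chronic skin condition, independent of treatment, including". Neither names sensitivity to sunlight or UV light.

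**The concern.** A risk-benefit section tells the ethics committee and participants which protections are in place. Here one of them is said to act during recruitment, but the recruitment rules do not contain it. A recruiter who applies 3.1 exactly as written could enrol someone with the very sensitivity that 6.2 says is looked for, and that person would be scheduled for three scans using UV light. What is at stake is participant protection and the accuracy of the risk statement. The estimates and error rates of the study are not at stake.

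**Working it through.** No arithmetic applies, so the check compares the sections in the order in which an applicant meets them.

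1. **What 6.2 requires.** A screen for sensitivity to light, placed in the recruitment process. The section does not say which form or person carries it out, or what follows a positive answer.

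2. **What the criteria in 3.1 ask.**
   - Inclusion: age, purchase of the product for 6 months, willingness to complete questionnaires, willingness to have all measurements, ability to attend the clinic.
   - Exclusion: conditions with regular medication, chronic skin conditions, recent collagen supplements, smoking, pregnancy or lactation, language, inability to consent, inability to follow procedures.
   - That is 5 inclusion and 8 exclusion items, and none of the 13 asks about light.

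3. **Whether a neighbouring item covers it.** The skin item names acne, eczema, psoriasis, rosacea and skin cancer. The medication item names lupus among other conditions. Both are introduced as non-exhaustive, so a chronic light-triggered skin disorder, or a medicated condition that brings light sensitivity with it, could fall under them. Each list is open only within its own heading, however. A person who reacts to light but has neither a chronic skin condition nor a condition requiring regular medication meets no exclusion.

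4. **Whether a later step covers it.**
   - Section 3.2 repeats the same inclusion and exclusion questionnaire at visit 1, so the second check adds no new criterion.
   - Section 3.3 describes a screening phone call and a medical questionnaire reviewed by a medical professional, but mentions no light-sensitivity question in either.
   - The sun-related questions in section 2.3 (sunscreen use, time in the sun) belong to the baseline questionnaire and serve the data analysis.
   - Appendix 1 shows the eligibility check at online screening and at visit 1, and no separate light-sensitivity check.

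5. **Result.** The screen is stated once, in 6.2. No criterion and no described procedure elsewhere in the protocol corresponds to it.

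**The case against.** The strongest reply is that the protocol does commit to the screen, in 6.2, and that the instruments which might carry it are not shown. The online form, the phone call, the medical questionnaire or the participant-characteristics entry at screening could each include the question. This stands as a limit. A reader might infer that the safeguard does not operate at all, but the documents do not show that; they show only that no written criterion or step delivers it. The reply does not close the gap, because 3.2 ties the decision to 3.1, and 3.1 gives a recruiter no basis for acting on such an answer.

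Second, a reader might take 6.2 to mean that light-sensitive people are excluded. It speaks of screening for sensitivity and states no exclusion, so a screen leading to a doctor's judgement would be compatible with it. That is correct, and it leaves the handling of a positive answer undefined as well.

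Third, other protections exist: a medical professional accompanies the measurements (6.2), and there is a rest period afterwards to make sure no reaction has occurred (3.3). These reduce the consequence. They act during or after the exposure, so they are not a substitute for a check that 6.2 places before it.

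Fourth, it is tempting to say that the risk category A classification depends on this screen. It does not: the justification in section 1 rests on the product's safety profile and on non-invasive measurements by trained personnel, and does not mention the screen.

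**Conclusion.** The inconsistency is real and should be corrected. Section 6.2 relies on a recruitment screen for which 3.1, 3.2, 3.3 and Appendix 1 provide no criterion or step, while each participant is scheduled for three scans using UV light. Indirect capture through the two open-ended exclusions is partial.

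The conclusion rests on the protocol text alone, with the forms and questionnaires unseen. Its size cannot be put in numbers: the documents give no share of light-sensitive applicants, and any percentage of the 60 participants would be a guess. A reader might also infer that light reactions would distort the Visia redness readings. For a scan to affect the next reading, a reaction would have to last one or two months, and nothing in the documents supports that. Sample size, power, error rates and the planned analysis are unaffected.

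**What to change.** Sections 3.1 to 3.3 and 6.2 must be reconciled, in one of two ways:

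- Carry the screen that 6.2 already states into the 3.1 list and into the inclusion and exclusion questionnaire, which is used online and again at visit 1. The sponsor and investigator would set, in writing, how a positive answer is handled; this review takes no position on that rule.
- Remove the statement from 6.2 and have the risk assessment judged without it.

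If an unshown form already asks the question, it is enough to name that form in 3.2 or 3.3 and add the matching entry in 3.1.

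The first option costs one line in 3.1 and one question in a form that already exists, and possibly a few fewer eligible applicants. The second costs a text change and a fresh look at the risk assessment. Neither changes the sample size or the analysis.
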